Spanish language skills to work effectively with that population. (2) Even if testing was conducted in Spain, it would require an additional sample separate from those currently associated with the clinical testing in order to avoid conflating the effects of the two interventions. (3) If testing were conducted in the UK, the extensive preparation and delay in gaining ethical approval to work with a clinical population (via the NHS) renders the task infeasible. For these and other reasons, we decided not to explore the "bridging" scenario, even though it holds strong potential on theoretical grounds. Nevertheless, we believe that if we test the social scenario and demonstrate its effectiveness, the joint findings of both the clinical intervention and the social intervention will show that the middle ground, the intersection between the two, is an effective and plausible way of combining the benefits of the ACANTO system. Thus, not testing the intersectional scenario is not an exclusion of an important test, but testing the system at the two ends of the spectrum (the clinical and social ends) shows that if both ends of the spectrum are successful, the intersection can be assumed to some extent.

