3.2.3 Design of the trial protocol

Firstly, a brief summary of the intervention will be helpful. There are two strands of the intervention: (1) testing of the social network and recommender system, and (2) testing of the FriWalk in a social context.

Testing the social network and recommendation system

The first part of the intervention, testing the social network and recommendation system, will involve recruiting a group of older adults to use the FriTab which contains the CPSN API installed. The CPSN will be populated with various events and participants will be asked to rate the quality of the recommendations. There will also be an event organised by the experimenters via the system to test how well it brings together people who have similar interests. We will test whether participants who use the social network and engage in the recommended activities are consequently more socially and physically active as a result of taking part (longitudinal comparison) and compared to a control group who do not take part (between-groups comparison).

Testing the FriWalk

The second part of the intervention will involve testing the FriWalk. To do this, an experimenter will set up a group activity via CPSN API for the FriTab (visiting the museum) to which numerous participants will be invited. Participants will receive a guided tour of the museum with the assistance of the FriWalk and the activity will be repeated on several occasions. We expect that this experience of using the FriWalk will reduce fear of falling while at the museum, will enhance the experience of visiting the museum, and will encourage bonding between the participants. These effects will be stronger for those using the FriWalk compared to those who (a) do not use the FriWalk in the museum, and (b) who do not attend the event.

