Then for the testing of the *FriWalk*. We intend to organise several events where users will come to a museum to test the FriWalk devices. It will involve an administrator/experimenter setting up an event and inviting users to come to the event. Users may be selected based on their stated interests (e.g. history) and may be matched based on their performance abilities (e.g. speed of walking). The experimenter will collaborate with a museum to arrange the event. UNAN has numerous museums that may be available for collaboration (e.g. Centre for Life, The Great North Museum, the Discovery Museum, or Segedunum Roman Fort).

The outcome measures are:

- 1. Physical activity
 - a. Step count: there should be an increased number of steps as a result of taking part in the activity
- 2. Psychological confidence
 - a. Fear of falling: Reduced fear of falling when using the device. This will be measured at baseline (T 1.2.4 questionnaires).

- b. Less anxiety about going out to attend an event where the FriWalk will be used
- 3. Social and emotional bonding
 - a. Sense of common identity: Social bonding/sense of shared identity as "FriWalk user group"
 - b. Increased perceived wellbeing as a result of shared identity (C. Haslam, Cruwys, and Haslam 2014; S. A. Haslam et al. 2009)
- 4. Improved ability to use the museum
 - a. Time taken to find facilities: it should be quicker for users who are unfamiliar with the environment to find facilities when they have the FriWalk.
- 5. Improved sleep quality
 - a. Subjective sleep quality: this should increase as a result of increase physical activity (see above (3b) for the rationale).

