- 10 participants will be used to test the FriWalk to tour the museum.
- 10 participants will be used to have a non-FriWalk based museum tour.
- 10 participants will be selected as a control group (no tour, no FriWalk).

Scales

The objectives listed above provide the conceptual variables that need to be measured. What follows is how we propose to measure them.

Control variables

Each of the control variables are taken from the UTAUT scale (Morris et al. 2003) and the items will be adaptations (for the ACANTO system) of these items. In the case of the social network testing, we will also ask about their engagement with the system to control for participants who were less interested in the system.

Variable	Scale/measure		
Perceived social involvement	Three items asking about the extent of perceived social involvement, its quality, and its enjoyability.		
Actual social involvement	In participant diaries, participants will list who they met during the day from outside the people who live in their home (1 item). This should be corroborated with data from the social network system.		
Quality of recommendations	Several items asking about the personal relevance of the recommendations, the liking of the recommendations, and the ability to do the recommendations.		
Turnout to experimenter- organised event	Number of people who attend event (recorded by experimenter)		
Liking of participants for one another	Several items asking to what extent they perceive others in the group as similar and the extent to which they like them.		
Physical activity	Number of steps taken as measured by step counters		
Well-being	Personal wellbeing index (International Wellbeing Group 2013)		
Perceived sleep quality	Pittsburgh Sleep Quality Index (Buysse et al. 1989)		

Table 7	. Social	l networl	k testing
---------	----------	-----------	-----------

Table	8.	Fri	Walk	testing
-------	----	-----	------	---------

Variable	Scale/measure	
Physical activity	Steps from step counters	
Fear of falling	Falls Efficacy Scale International Short form (Kempen et al. 2008)	
Anxiety about attending event	Several items asking extent to which the user feels anxious about attending events outside the home (baseline) and the extent to which they feel anxious attending events where a FriWalk is available. Anxiety will be asked with reference to (a) finding their way around the environment and (b) having physical support.	

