Test event	To test the system, the experimenters will run an interactive workshop and will advertise it via the ACANTO social network. The topic of this workshop is to be decided, but it may be something like, "A guide to smartphones for the older user." The activity will be tagged with relevant tags (e.g. "technology", "internet") and users who express these interests should receive a recommendation for the workshop. Turnout will be monitored at the event and liking for others in the group will be assessed.	
Return and debrief	After the 2 weeks, all participants will return and be debriefed on the purpose of the study. Additional measures will be taken via a short questionnaire (to see changes from the questionnaire administered at the start of the study).	

Table 10. Phases of FriWalk study

	Phase 1: Ethics, recruitment and collaboration
Ethics	Ensure ethical approval is obtained from UNAN ethics procedure
Recruitment	Recruit interested participants to take part in the FriWalk trial.
Collaboration	Collaboration with museums to implement FriWalk devices in the environment.
	Phase 2: Pilot testing
Testing at UNAN	Devices will be set up on UNAN premises and participants will be invited to try out the devices. Data will be collected about users' average walking pace to assist with matching participants for the museum trial.
Baseline tracking	Participants will be given diaries and step counters to monitor their baseline activity.
	Phase 3: Museum testing
Museum tour start	 Participants will be invited to a tour of a museum where they will be given a FriWalk. Approximately 4 participants will be in each group, assuming that 4 FriWalk devices will be available. Each group will be tested on separate days. Some of these events may be advertised via the social network system. Participants may be matched based on their average walking pace or ability.

Pre-tour questionnaire	Questionnaires will be completed before the tour.
Tour	The tour will involve a programmed route during which the FriWalk will guide the user around the museum. An experimenter will accompany the participants.
Post-tour questionnaire	After the tour, a questionnaire will be completed to ask about the experience.
Control group	A tour will be arranged without the FriWalk and will act as a control group. Questionnaires will be completed before and after.
Second control group	Participants in the no-tour, no-FriWalk group will attend the university to provide answers to a questionnaire.

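### Network exposure can differ between the three museum groups, so FriWalk differences in steps, well-being and sleep may not be separable from social-network effects

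*Protocol*

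**What the plan says.** The social trial tests two things: the social network with its recommendations (CPSN, used on the FriTab), and the FriWalk on museum tours.

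- **Set-up of the tours.** In Section 3.2.3, under the testing of the FriWalk, "an experimenter will set up a group activity via CPSN API for the FriTab (visiting the museum) to which numerous participants will be invited". This is worded as a plan.
- **Advertising.** In Table 10 (Section 3.2.3.4), the row that starts the FriWalk tour says "Some of these events may be advertised via the social network system". This is worded as an option, for part of the events.
- **Selection.** Section 3.2.3.1 says of the museum events: "Users may be selected based on their stated interests (e.g. history", with matching on walking ability also possible.
- **Groups.** Section 3.2.3.4 lists three: "10 participants will be used to test the FriWalk to tour the museum"; "10 participants will be used to have a non-FriWalk based museum tour"; and "10 participants will be selected as a control group (no tour, no FriWalk". No random allocation is stated.
- **Comparison groups.** Table 10 says of the first only "A tour will be arranged without the FriWalk and will act as a control group". The second attends the university to answer a questionnaire. No network route is given for either.
- **Sample.** Section 3.2.3.2 describes one source for the whole social trial: people already in the longitudinal tracking task, plus new recruits. It has no rule against taking part in both studies.
- **Outcomes.** Tables 7 and 8 share three measures: step counts, the Personal Wellbeing Index and the Pittsburgh Sleep Quality Index.
- **Analysis.** Section 3.2.6 compares the FriWalk groups by ANOVA. It does not name network use as a factor in that comparison.

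**The concern.** The network is an active intervention in this protocol. Section 3.2.3.1 predicts that its users will walk more and, as a result, report better well-being and sleep. If the FriWalk group contains more network users than a comparison group, part of any difference on these three outcomes is what the protocol itself expects from the network. The museum study could then credit the device with a benefit that came from the network.

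The sponsor has recognised this kind of problem elsewhere. Section 3.2.1 says that testing a combined clinical and social use in Spain would need a separate sample "in order to avoid conflating the effects of the two interventions". No comparable separation is set out for the two social interventions.

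Invitation route and sample overlap are fixed at recruitment. If every FriWalk participant used the network and no control did, group and network use would be the same variable, and no later analysis could separate them.

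**Working it through.** **Step 1. What the protocol says about network exposure in each museum group**

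| Group | n | Network link in the text |
|---|---|---|
| FriWalk tour | 10 | Activity set up via the CPSN (3.2.3); some events may be advertised there (Table 10) |
| Tour without FriWalk | 10 | None given; the tour is arranged |
| No tour, no FriWalk | 10 | None given; people are selected |

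The only stated network route attaches to the FriWalk tour. With 10 per group, each person's network status moves a group's exposure share by 1/10 = 10 percentage points.

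**Step 2. Which outcomes are exposed**

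Table 8 lists eight measures. Three are also in Table 7: steps, well-being and sleep quality. The other 8 - 3 = 5 are fear of falling, anxiety about attending, common identity, time to find facilities and willingness to return. The protocol does not name these as network outcomes, so they are less affected.

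**Step 3. Form of the bias**

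Let p1 be the share of network users in the FriWalk group, p0 the share in the comparator, N the network effect in SD units and C the intended contrast. If the effects add, the expected difference is

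C + (p1 - p0) × N.

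The second term is the bias. It is zero when p1 = p0. The protocol gives none of p1, p0 and N, nor any effect size or SD for the social studies. There is no planned figure to reproduce, and the actual bias cannot be computed.

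**Step 4. Illustration on assumed values**

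Assume C = 0 and a two-sided two-sample t-test with 10 per group (18 degrees of freedom), standing in for the ANOVA. The level of 0.05 is also an assumption: Section 3.1.4 sets it for the clinical trial, and Section 3.2.6 sets none. The noncentrality is bias / √(1/10 + 1/10) = 2.236 × bias. For a gap of 0.50 and N = 0.5 SD, the bias is 0.50 × 0.5 = 0.25 SD, the noncentrality is 0.559 and the rejection rate is 8.3%.

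| Assumed N | Gap 0.25 | Gap 0.50 | Gap 1.00 |
|---|---|---|---|
| 0.2 SD | 0.05 SD; 5.1% | 0.10 SD; 5.5% | 0.20 SD; 7.1% |
| 0.5 SD | 0.125 SD; 5.8% | 0.25 SD; 8.3% | 0.50 SD; 18.5% |
| 0.8 SD | 0.20 SD; 7.1% | 0.40 SD; 13.5% | 0.80 SD; 39.5% |

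Each cell gives the bias and the false-positive rate. With no gap the rate is 5%.

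**Step 5. The network study**

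It has 15 + 15 = 30 users, 15 controls without the network, a 2-week window and its own test event, a workshop (Table 9). Section 3.2.4 lists completion of network testing (MS7) before completion of tour testing (MS8), without dates. FriWalk use enters its outcomes only if a network user takes a tour inside the 2 weeks. Nothing places a tour there, and nothing forbids it.

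**The case against.** The case on the other side has real force.

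- **Mixing is permitted, not planned.** Advertising is optional and covers some events. The FriWalk study has its own recruitment row in Table 10, and the second use case has its user simply invited. No text says that museum participants come from the network study, and a shared source is not the same as shared people. This stands: unequal exposure is possible and unprevented, but not established.
- **The tour-versus-tour contrast may be clean.** It is biased only if exposure differs between the two tour groups, which the text does not state. This stands, and it is why the concern is clearest against the no-tour group.
- **Baseline data help.** Table 10 gives baseline diaries and step counters, and questionnaires before and after both kinds of tour. A stable effect of earlier network use would largely cancel in within-person change. This stands in part: an effect that starts or fades between the two measurements would not cancel, and the no-tour row mentions only one questionnaire attendance.
- **Exposure could be recovered.** Table 6 asks for access to user data, and Section 3.2.5 plans to match participant data. A statistical analysis plan, not at hand, might adjust for network use. This helps with partial imbalance only.
- **Section 3.2.1 is not a general rule.** It gives one reason among several for leaving out a clinical-social bridge, so the social trial does not contradict it.

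A reader might infer that the two effects are mixed in both social studies, for instance that 10 of 30 network users (33%) against 0 of 15 controls would have a FriWalk tour counted in the 2-week totals. The documents do not support that. The figure needs every FriWalk participant to be a network user touring inside the window. Attending advertised events is also part of how the network is meant to work, so only the added FriWalk use would contaminate.

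**Conclusion.** The concern holds for the museum study in a limited form. The protocol ties the FriWalk tour to the network, gives the comparison groups no network route, states no random allocation and does not require separate samples. Network exposure can therefore differ between groups, and FriWalk differences in steps, the Personal Wellbeing Index and the Pittsburgh Sleep Quality Index may not be separable from network effects. The five other measures in Table 8 are less affected.

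The size is unknown. On the assumed values above, the false-positive rate runs from 5.1%, which is negligible, to 39.5% with complete separation and a 0.8 SD network effect. These figures assume additive effects and no FriWalk effect. Complete inseparability is the extreme case, and nothing in the protocol says it will occur. Contamination of the network study is a secondary possibility, confined to tours inside its 2-week window. The point merits a change before recruitment because the change is cheap and full imbalance could not be repaired afterwards.

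**What to change.** In Section 3.2.3 and Table 10:

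1. Invite all three museum groups by the same route and with the same network status. People outside the network study are preferable. Otherwise, put the same mix of network users and non-users in each group, entered only after the network debrief.
2. Do not list study tours on the CPSN until the 2-week network test is complete.
3. Record network use for every museum participant and include it in the FriWalk comparison.

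Restricting all groups to people who finished the network study is not practical: 10 + 10 + 10 = 30 museum places would need all 15 + 15 = 30 network users.

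The cost is protocol wording, the order of invitations and one recorded item. The small downside is that the route from network to tour is shown only outside the comparison, or is offered equally to all three groups.

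### In the museum study the no-tour group has one questionnaire of unstated timing, so before-after change on questionnaire outcomes cannot be compared with that group

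*Protocol*

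**What the plan says.** The museum study has three groups of equal size (section 3.2.3.4, recruitment for the FriWalk study). For the first, the text reads: "10 participants will be used to test the FriWalk to tour the museum". The second group, also of 10, visits without the device, and the third, again of 10, has neither tour nor device.

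Table 10 sets the questionnaire schedule:

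- **FriWalk tour:** "Questionnaires will be completed before the tour", and a further questionnaire about the experience follows the tour.
- **Tour without FriWalk:** "Questionnaires will be completed before and after".
- **No tour, no FriWalk:** "Participants in the no-tour, no-FriWalk group will attend the university to provide answers to a questionnaire".

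Section 3.2.3, under the testing of the FriWalk, expects less fear of falling, a better visit and bonding. It expects these effects to be stronger with the FriWalk than in people who tour without it and in people who do not attend. Section 3.2.3.1 words the questionnaire outcomes as reductions or increases: less fear of falling, less anxiety, more well-being, better sleep.

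On baselines, section 3.2.3.1 says of fear of falling: "This will be measured at baseline (T 1.2.4 questionnaires"). Section 3.2.3.2 says that only some participants come from task 1.2.4 and that others are newly recruited. In Table 8, the anxiety baseline asks about events away from home in general, and the companion item asks about "the extent to which they feel anxious attending events where a FriWalk is available".

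**The concern.** The no-tour group is there to show what happens to these outcomes without a visit. To do that for an outcome worded as change, it needs a first and a second value on the same scale. Table 10 mentions one questionnaire for this group and does not say whether it falls at the start or at the end.

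Nothing else in the section clearly supplies the missing value. The Phase 2 baseline tracking consists of diaries and step counters, and it does not name fear of falling, anxiety, well-being or sleep. The task 1.2.4 questionnaires may supply an earlier fear-of-falling score, but only for those who took part in that task.

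At stake is the second of the two predicted contrasts, FriWalk users against non-attenders. With one value per person, a difference that existed before the study cannot be told apart from an effect of the tour. An analysis plan can choose the model, but it cannot recover a measurement that was never taken.

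**Working it through.** The protocol gives no power calculation, effect size, standard deviation or correlation for the museum study, so there is no stated figure to reproduce. The check is first a comparison of the schedule, then a calculation for scale.

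**1. Questionnaire occasions (Table 10).** FriWalk tour 2; tour without FriWalk 2; no tour 1. The total is 3 × 10 = 30 participants. From Table 10 alone, 0 of the 10 no-tour participants have a before-after pair.

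**2. What other sources could add for the no-tour group.** This takes the Table 8 scales to be carried by the Table 10 questionnaires.

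| Outcome | First value available? |
|---|---|
| Step count | Yes: Phase 2 tracking excludes no group |
| Fear of falling | For 0 to 10 of the 10, because the share from task 1.2.4 is not stated for this study |
| Well-being | None stated |
| Sleep quality | None stated |
| General anxiety | None stated |

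**3. Allocation.** Controls are described as selected. FriWalk users may be chosen by interest and matched on walking pace (section 3.2.3.1, Table 10). No random allocation is described, so similarity at baseline cannot be presumed.

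**4. Precision of a follow-up-only comparison (illustration).** Inputs: n = 10 per group from section 3.2.3.4; outcome SD set to 1; baseline-to-follow-up correlation r assumed.

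- Standard error of a pairwise difference, follow-up only: √(2/10) = 0.447 SD.
- Adjusted for baseline: 0.447 × √(1 − r²).
- Share of information lost without baseline: 1 − (1 − r²) = r².
- Detectable difference at an assumed 80% power and two-sided 0.05 (normal approximation): (1.96 + 0.84) × standard error.

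| r (assumed) | SE, adjusted | Information lost | Detectable, adjusted |
|---|---|---|---|
| 0.3 | 0.427 | 9% | 1.20 SD |
| 0.5 | 0.387 | 25% | 1.09 SD |
| 0.7 | 0.319 | 49% | 0.89 SD |
| 0.8 | 0.268 | 64% | 0.75 SD |

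Follow-up only, the detectable difference is about 1.25 SD whatever r is.

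**5. Bias.** A pre-existing gap of d SD between groups carries into the follow-up comparison as about r × d. A gap of one standard error, 0.447 SD, could arise by chance even in randomised groups of 10. At r = 0.7 it would appear as 0.7 × 0.447 = 0.31 SD of apparent effect. Selected groups may differ by more.

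**The case against.** A reader might infer that change cannot be compared across the three groups at all. The text does not support that. Step counts, the first listed FriWalk outcome, have a baseline phase open to all participants. The two tour groups both have before and after questionnaires, so the contrast that isolates the device is intact.

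A reader might also infer that new recruits will have no fear-of-falling baseline, or that the gap differs by group. The reference to task 1.2.4 could mean the instrument used or values already collected, and nothing says that new recruits will not be given it. The split of tracked and new participants is not stated for this study, so no difference by group is shown. Where earlier values exist, they help the no-tour comparison.

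The two anxiety items could be read as a wording error. Section 3.2.3.1 states the objective as less anxiety about events where the FriWalk is used, and the two items partly express that intended contrast. What remains is narrower: the difference between the two items is not a change over time, and the protocol does not say that the general item is repeated.

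Table 10 is also terse. It does not state that the no-tour group attends only once, and it does not list the scales in the post-tour form. Section 3.2.6 names a before-after comparison only for the social network study. For the FriWalk it names experimental against control groups, which can be run on one value per person. Some outcomes, such as time to find facilities, willingness to return and fear of falling while at the museum, have no no-tour counterpart, so a second questionnaire would not supply one.

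All of this narrows the point. It does not remove the mismatch between a predicted change relative to non-attenders and the single questionnaire listed for them.

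**Conclusion.** The point holds in limited form. As written, before-after change in well-being, sleep quality and general anxiety cannot be compared with the no-tour group. The same goes for fear of falling, except possibly in task 1.2.4 members. A follow-up-only comparison is possible, but it rests on groups of 10 being comparable at baseline when no random allocation is described.

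The loss of precision runs from 9% to 64% for r from 0.3 to 0.8. No single figure in that range can be attributed to the protocol, which gives no correlation. The exposure to bias does not depend on knowing r exactly: any r above zero lets a baseline gap through.

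This concerns the second control group of a small study and leaves the other contrasts as they are. It is a cheap improvement that must be made before data collection.

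**What to change.** - In Table 10, give the no-tour group the same questionnaire on two occasions, at an interval matched to the tour groups' before and after. List the scales that each occasion contains.
- Take the fear-of-falling baseline from that first matched questionnaire for all 30 participants, so that it does not depend on membership of task 1.2.4.
- Ask the general anxiety item, in identical wording, on both occasions in all three groups. Keep the FriWalk-specific item as an addition.
- Compare groups on the follow-up value adjusted for baseline. The model details can sit in the analysis plan.

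The cost is one more short questionnaire for 10 people and a few repeated items for the rest. Adjustment reduces measured baseline differences, but it does not replace random allocation, so the no-tour contrast should still be reported with that caution.
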